Addiction Severity Index-6th Edition Modified Version (ASI6-Modified): The ASI is a multi-dimensional interview used to measure the substance use, health, and social problems of those with alcohol and other drug problems, both at admission to treatment and subsequently at follow-up contacts (McLellan et al., 1992; McLellan et al., 1980). We are using an abbreviated version of the ASI-6 that eliminates many of

the items that do not contribute to our primary hypotheses and takes approximately 20 minutes to complete. We will use only the ASI domains for medical, drug use, alcohol use, and psychological status for covariate analysis. The ASI-6 produces *Recent Status Scores* in each of these four areas, which have demonstrated high levels of inter-rater, test-retest, and concurrent reliability (Cacciola et al., 2011). Our modified version also includes items from the QDS (see above) in order to obtain consistent and reliable estimates of alcohol use. *Administered at BL, 3 months, and 6 months.*

**EQ-5D-5L:** The EQ-5D™, a trade mark of the EuroQol Group, is a standardized measure of health outcomes. It takes only a few minutes to complete, and it provides a simple descriptive profile and a single index value for health status. *Administered at BL, 6 weeks, 3 months, 6 months.*

**Client Shared Decision Making Questionnaire:** The Shared Decision Making Questionnaire (SDM-Q client version; Kriston et al., 2010) is a validated 9-item questionnaire that measures the process of shared decision making between clinicians and patients. We adapted this measure to apply to substance abuse treatment decision making. This version of the questionnaire measures shared decision making from the patient's perspective. *Administered at BL, 6 weeks, 3 months, 6 months.*

**Client Satisfaction Questionnaire:** The Client Satisfaction Questionnaire was developed for this study and assesses the extent to which participants perceived the intervention to be helpful and useful. It contains both closed- and open-ended questions in order to obtain information that will help us further refine the intervention for dissemination. *Administered at 3 months only.*

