## Data Analysis Plan

**Data Management and Analysis-** All interview and self-report measures will be completed via a web-based data entry program that has been used at TRI and the University of Pennsylvania for the past 5 years. Direct data entry reduces errors that can occur when transferring information from paper forms into electronic files. See our Data Management Plan for data integrity procedures. Prior to performing analyses, standard data screening/cleaning procedures will be applied: re-screening the data for data-entry errors, assessing the extent and pattern of missing data, and checking that appropriate assumptions of normality are met, employing remedial measures when necessary. We will check to confirm that the groups do not differ at baseline on relevant background variables using analyses of variance (ANOVA) for continuous variables and log-linear models for discrete or ordinal responses. The randomization process should minimize the need for the inclusion of covariates to reduce bias in the treatment comparisons. However, relevant covariates will be considered for inclusion in the analyses to improve the precision of estimation of the effects .

**Exploratory Hypothesis 1: Patients in the TK Condition will** participate in shared decision making conversations with their counselors at higher rates than patients randomized to **TAU**. Number of sessions in which patients indicate that their counselors conducted a shared-decision making conversation at the 6-week and 3-month follow-up will be examined. Average number of sessions per patient will be compared at the 6-weeks and 3-month follow-up point. We will calculate effect sizes between conditions using Cohen's d. Quality of shared decision making conversations will be calculated using a subscale of the fidelity checklist. Differences in patient perceived quality will be averaged, and effect sizes will be calculated using Cohen's d.

**Exploratory Hypothesis 2: Patients in the TK will report greater satisfaction and acceptability with their individual sessions than patients randomized to TAU.** Scores on the Patient Satisfaction measure will be averaged and compared between conditions for the assessment at the three-month follow-up point. We will calculate overall Satisfaction rating and Satisfaction with the Referred Services Subscale score. We will calculate effect sizes using Cohen's d.

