**Exploratory Hypothesis 3: Patients in the TK condition will demonstrate increased alcohol and drug abstinence (UA verified) and fewer days of self-reported alcohol and drug use during treatment and at follow-up than TAU patients.** We will compare rates of urinalysis-confirmed abstinence in the two groups at weeks 6 and 12.. The model will include terms for group, time, and their interaction, and baseline urine result along with any other necessary variables will be included as covariates. We will also compare days of self-reported alcohol and drug use based on the TLFB completed at the 6- and 12--week assessments. We will examine mean differences in abstinence rates and days of use, and estimate effect sizes using Cohen's d.

**Exploratory Hypothesis 4: Patients assigned to the TK condition will demonstrate improved ASI Alcohol Severity Scores relative to patients assigned to TAU.** We will calculate the ASI Alcohol Severity Score for patients in each condition, and examine change scores from baseline to 3-months. We will examine size of effect between condition change scores using Cohen's d.

**Exploratory Hypothesis 5: Patients assigned to the TK condition will demonstrate higher rates of engagement in substance abuse treatment than patients assigned to TAU.** Patients in the two groups will be compared on the number of treatment sessions attended in the past 90 days at the 3-month assessment. We will estimate size of effect differences on retention using Cohen's d.

**Exploratory Hypothesis 6: Patients assigned to the TK condition will demonstrate higher rates of Vivitrol initiation than patients assigned to TAU.** A logistic regression model will be used to compare patients in the two groups on initiation rates at the 3-month assessment. Patients will be considered MAT initiated if they receive a Vivitrol injection during the relevant time period, or if they attended an evaluation for Vivitrol and were deemed inappropriate for Vivitrol and referred to an alternative MAT.

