**Missing Data:** As recommended by Lavori , we will analyze the data under an intent-to-treat principle in which all patients initially randomized will be included. We will characterize the group of patients who drop out before the end of the study using logistic regression models to relate dropout to these characteristics. These characteristics will be drawn from the data gathered during the study. These analyses will allow us to determine whether the drop out process is completely at random. We cannot test whether the process is missing at random (i.e. drop-out independent of values of

missed responses, conditional on covariates and observed responses), but we will attempt to obtain information on the reason for drop out. The mixed effects models will accommodate some missing data and drop out. We will examine simple pattern mixture models to assess whether the longitudinal missing data are ignorable.

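### H4 is analysed on raw change scores and H3 days of use on follow-up means, with no baseline or site term fixed; baseline adjustment is usually, not always, more precise, and the SD behind the H4 effect size should be named

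*SAP*

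**What the plan says.** SAP, Data Analysis Plan, Exploratory Hypothesis 4: "We will calculate the ASI Alcohol Severity Score for patients in each condition, and examine change scores from baseline to 3-months". The effect measure follows: "We will examine size of effect between condition change scores using Cohen's d". No model and no covariate are given.

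SAP, Exploratory Hypothesis 3, days of use: the data are "based on the TLFB completed at the 6- and 12--week assessments", and the analysis is "We will examine mean differences in abstinence rates and days of use", again with Cohen's d. A baseline covariate is fixed in one place only. The group-by-time model that follows the urinalysis endpoint says "baseline urine result along with any other necessary variables will be included as covariates". It names neither baseline days of use nor site.

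Elsewhere the plan leaves adjustment open:

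- The SAP's opening paragraph says "relevant covariates will be considered for inclusion in the analyses to improve the precision of estimation of the effects".
- The SAP's Missing Data paragraph says "The mixed effects models will accommodate some missing data and drop out", but no mixed model is set out for H4 or for days of use.
- Protocol section 7, under the ASI6-Modified, says "We will use only the ASI domains for medical, drug use, alcohol use, and psychological status for covariate analysis", without tying these domains to an outcome or model.

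The same entry schedules the ASI at baseline and at 3 months. Protocol section 6 randomizes counselors within sites. The SAP names site in no analysis.

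**The concern.** A change score uses the baseline with its coefficient fixed at 1. A follow-up mean uses it with its coefficient fixed at 0. A regression on baseline estimates the coefficient and so usually leaves less residual variance. Site is the randomization stratum and would ordinarily be in the model.

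For H4 there is also a question of scale. Read literally, the d divides by the SD of change, and that SD depends on the correlation between visits. One true effect can therefore appear as quite different values of d. Protocol section 5 disclaims power and makes effect sizes for a future, fully powered trial the purpose of the data, so width and scale of these estimates are what the study delivers. Protocol section 6 also records that the funder ended recruitment, so the sample may be smaller than planned.

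**Working it through.** The documents give no SD, correlation, target effect, alpha or power, so there is no figure of the plan's own to reproduce.

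**Inputs.** From the documents: 25 patients per condition, clients from two sites (Protocol section 4). Assumed: r, the baseline-to-follow-up correlation, at 0.3, 0.5 and 0.7; k, baseline SD divided by follow-up SD, at 0.7, 1 and 1.3; no clustering. A case of 10 per arm is assumed, to see what early closure could do. The follow-up SD is set to 1.

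**Variance per patient.** Change score: 1 + k² − 2rk. Follow-up mean: 1. Baseline-adjusted: 1 − r².

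**95% half-widths**, m per arm, N = 2m:

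- change: t(N−2) × √[(1 + k² − 2rk) × 2/m]
- follow-up mean: t(N−2) × √(2/m)
- adjusted: t(N−4) × √[(1 − r²) × (2/m) × (1 + 2/(N−5))], which pays for baseline and site

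At m = 25, t is 2.0106 and 2.0129 and the inflation factor is 1 + 2/45 = 1.0444. At m = 10, t is 2.1009 and 2.1199 and the factor is 1 + 2/15 = 1.1333. Example for m = 25, r = 0.5, k = 1: change 2.0106 × √(1 × 0.08) = 0.569; adjusted 2.0129 × √(0.75 × 0.08 × 1.0444) = 0.504; ratio 0.886, so 11% narrower.

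**H4, 25 per arm**

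| | r = 0.3 | r = 0.5 | r = 0.7 |
|---|---|---|---|
| Adjusted (any k) | 0.555 | 0.504 | 0.416 |
| Change, k = 0.7 | 0.588 | 0.505 | 0.406 |
| Change, k = 1 | 0.673 | 0.569 | 0.441 |
| Change, k = 1.3 | 0.786 | 0.670 | 0.530 |
| Adjusted vs change, k = 0.7 | 6% narrower | tied | 2% wider |
| Adjusted vs change, k = 1 | 18% narrower | 11% narrower | 6% narrower |
| Adjusted vs change, k = 1.3 | 29% narrower | 25% narrower | 22% narrower |

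**H4, assumed 10 per arm.** Adjusted: 0.963, 0.874, 0.721. Change at k = 0.7: 0.972, 0.835, 0.671, so adjustment is 1% narrower, then 5% and 7% wider. Change at k = 1: 1.112, 0.940, 0.728. There the adjusted interval becomes the wider one once r exceeds about 0.73; at 25 per arm that point is about 0.91.

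**H3 days of use.** The follow-up mean has half-width 0.569 at 25 per arm, against the same adjusted values. The gain is 2% at r = 0.3, 11% at 0.5 and 27% at 0.7. Setting the two half-widths equal gives r of about 0.21; below that, adjustment loses. At 10 per arm the follow-up mean has 0.940 and the break-even r is about 0.37.

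**Scale of the H4 d.** At k = 1 the SD of change is √(2 − 2r), so a true difference of 0.5 follow-up SD gives 0.5/√1.4 = 0.42, 0.5/√1.0 = 0.50 and 0.5/√0.6 = 0.65. Over the follow-up SD it stays 0.50. With n per arm = 2 × (1.960 + 0.842)²/d² (two-sided 0.05, 80% power), those values imply 88, 63 and 38 per arm. A planner who took 0.65 into a trial analysed on follow-up scores would enrol 38 per arm where 63 are needed, with power just under 60%.

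**The case against.** The strongest reply is that the plan already allows for this. The SAP says covariates will be considered, and for the same reason: precision. The protocol keeps ASI domains for covariate use, and the SAP speaks of mixed models in the plural. The study is exploratory and unpowered. That is fair, and it rules out saying that the plan ignores adjustment. It does not remove the point. H4 has a specific stated method, and an openness to covariates does not say which ones enter or replace the change score.

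A second reply is that the gain depends on values nobody has. This stands. Eligibility requires an AUDIT score of at least 16 and 6 recent drinking days (Protocol section 9), which could reduce the baseline spread and so lower k, and could lower r for drinking days. The gain may then be small or slightly negative. Days of use may also be skewed, which these formulas ignore; the SAP does promise normality checks and remedies.

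Some stronger readings do not hold:

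- A reader might infer bias. Under sound randomization both planned estimates are unbiased.
- A reader might infer that every d lacks a usable SD. A conventional two-group d on H3 days already divides by the pooled follow-up SD, so the scale problem is confined to H4.
- A reader might infer that adjustment always helps, or helps unless k is close to r. In small samples the loss extends further, as the 10-per-arm results show.
- A reader might infer a demonstrated gain from the site term. Here site is only charged for; the case for it is that it is the stratum.

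**Conclusion.** The point holds as a recommended improvement in precision and reporting. At the planned 25 per arm, over the r and k examined and without clustering, the adjusted H4 interval ranges from 29% narrower to 2% wider than the change-score interval. For H3 days the benefit is about 2% at r = 0.3 and turns negative below about 0.21. The firmer part is the scale of the H4 d: the same true 0.5 SD effect can read anywhere from 0.42 to 0.65 at equal SDs, and a later planner cannot undo that without knowing the SD and r.

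Everything numerical rests on assumed r and k. Counselor clustering and the H3 instrument conflict are separate matters; they enter here only because the recommended models have to be compatible with how they are resolved.

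**What to change.** **H4.** Model the 3-month ASI Alcohol score on arm, baseline ASI Alcohol score and site, allowing for counselor as the randomized unit. Report the adjusted difference with a 95% CI. State that d uses the pooled within-arm follow-up SD, not the SD of change. Report the baseline SD, the follow-up SD and r, so that the next trial can be sized for whichever analysis it uses.

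**H3 days of use.** First reconcile the instruments. The SAP relies on a TLFB at 6 and 12 weeks. Protocol section 7 instead lists QDS and ASI drug items at 6 weeks and a modified ASI with QDS items at baseline and 3 months. The protocol plans a TLFB only at screening, in section 9. Then adjust for baseline days from the matching instrument, and for site.

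**Cost.** H4 needs SAP wording only, because both ASI assessments are already scheduled. Baseline and site use two degrees of freedom. If far fewer patients were enrolled, for example the assumed 10 per arm, the adjusted interval can be up to about 7% wider than the change score at k = 0.7, and is wider at k = 1 once r exceeds about 0.73. With few patients per counselor the counselor variance may be poorly estimated, and the report should say so if it is. Recruitment is already described as ended, so a change made after data were seen should be labelled post hoc.

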## 2. Specific aim(s)

**Aim 1:** An existing evidence-based toolkit intervention will be adapted and redesigned by a patient and provider team into an engaging, narrative graphic novel curriculum useful in substance abuse counseling. The proven behavioral interventions will be augmented with health education material focused on MAT and HIV risk reduction. Together, these materials will comprise the Health Education Toolkit. The Health Education Toolkit (**TK**) will employ a shared decision making model to encourage 1) increased recovery engagement by patients, and 2) patient engagement in deciding whether to initiate and adhere to MAT.

**Aim 2:** We will provide training and support to increase patient access to MAT for alcohol-related SUDs at a centrally located Federally Qualified Healthcare Center.

**Aim 3:** We will assess the feasibility and acceptability of the HET Toolkit to estimate whether exposure to the Toolkit (**TK**) can reduce substance use and increase engagement with MAT. We will conduct a three-month, randomized controlled trial of 50 patients with active alcohol SUDs enrolled in inpatient and outpatient treatment to obtain estimates of effect on the following exploratory hypotheses:

**Exploratory Hypothesis 1:** Patients randomized to the **TK** will participate in shared decision making conversations with their counselors at higher rates than patients randomized to treatment-as-usual sessions (**TAU**).

**Exploratory Hypothesis 2:** Patients randomized to the **TK** will report greater satisfaction and acceptability with their individual sessions than patients randomized to **TAU**.

**Exploratory Hypothesis 3:** Patients randomized to **TK** treatment sessions will demonstrate a) larger reductions in substance use (drug and alcohol) and b) increases in abstinence measured by urine-confirmed, self-reported days using over the 3-month follow-up compared to patients randomized to **TAU**.

**Exploratory Hypothesis 4:** Patients assigned to the **TK** condition will demonstrate improved ASI Alcohol Severity Scores relative to patients assigned to **TAU**.

**Exploratory Hypothesis 5:** Patients randomized to **TK** will attend more specialty substance abuse intervention and treatment sessions over the 3-month follow-up period than patients randomized to **TAU**.

**Exploratory Hypothesis 6:** Patients randomized to **TK** will initiate MAT for alcohol dependence at greater rates than patients randomized to **TAU**.

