#### Expanding Patient Access to MAT

Few community treatment programs (including some that will serve as research sites for this study) offer MAT as a treatment option for patients. As part of this project, we will work with the Public Health Management Corporation's (PHMC) Care Clinic to offer MAT for alcohol SUDs. PHMC is a regional public health institute that serves close to 200,000 patients annually and includes more than 250 programs in 70 locations, one of which is the Care Clinic, a Federally Qualified Health Center (FQHC) where study patients may be referred. The medical staff at the Care Clinic will establish a routine protocol for treating patients with Vivitrol. Staff at the Care Clinic will evaluate patients for suitability following standard medical guidelines, and dispense Vivitrol to study participants as well as non-study patients provided the patient is suitable, medically eligible, and is covered by their insurance. Behavioral health staff will interview prospective patients to determine whether they are suitable for Vivitrol MAT, and medical staff will oversee their medical treatment. It is important to note that this protocol at the Care Clinic will not be considered research, or part of the present research project. The purpose of our research is to determine whether patients exposed to the Health Education Toolkit in a SUD treatment setting become more likely to seek out and initiate MAT for alcohol SUDs. No patient will be assigned to Vivitrol, or asked to take it as part of this protocol. With a patient participant's permission, our team will be given a release to confirm when study participants are evaluated for and initiated on Vivitrol, but this permission is at the patient's discretion and not mandatory to participate in the current research project.

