**Patient Outcomes**

Quick Drinking Screen and ASI Drug Grid: This instrument contains items from two established instruments: the Quick Drinking Screen (QDS), and the Addiction Severity Index (ASI). The QDS is a six question screener that estimates the frequency and quantity of drinking. Two comparison studies found high levels of agreement between the QDS and the Timeline Followback, the “gold standard” in drinking measurement (Roy et al. 2008, Sobell et al, 2003). We also included the Follow-up Assessment Drug Grid and overall drug use questions from the ASI (see below) in order to assess for both alcohol use and other substance use. *Administered at 6 weeks only*.

Urine testing: Urine drug testing will be done using kits that test for cocaine, opiates, amphetamines, methamphetamines, benzodiazepines, cannabis, barbiturates, and PCP. These will be purchased from ACON International. These kits provide a rapid (5-minute) on-site urine test. *Administered at BL, 6 weeks, 3 months, 6 months*.

Non-Study Medical and Other Services (NSMOS): This questionnaire was adapted from the Treatment Services Review (McLellan et al., 1992) for patients in medical settings. The NSMOS counts substance abuse treatment, medical services, visits to medical offices, hospitalizations, and emergency room visits received that were not a part of the assigned treatment. *Administered at BL, 6 weeks, 3 months, 6 months*.

PHMC Utilization Review: PHMC Care Clinic will maintain records on patients from the study who are referred for Vivitrol evaluation. By prior patient consent, the Care Clinic will release records on whether a study patient attended an appointment for a Vivitrol evaluation, the determination of appropriateness for Vivitrol, and whether the patient actually received the initial dose and subsequent doses (if any) of medication.

HIV Risk Assessment (HIV-RA): The HIV Risk Assessment provides a brief self-report measure of HIV testing history and sexual risk and uses the preceding three months as the time interval of interest. The HIV-RA was developed [name], and [name], experts in the field of HIV risk behaviors. *Administered at BL, 6 weeks, 3 months, 6 months*.

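### SAP Hypothesis 6 scores evaluated-and-referred patients as MAT initiated, so its rate is neither Vivitrol initiation (the SAP heading) nor MAT initiation (the protocol)

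*SAP*

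**What the plan says.** Three texts describe the outcome for Hypothesis 6.

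- **Protocol, section 2, Exploratory Hypothesis 6:** TK patients "will initiate MAT for alcohol dependence at greater rates than patients randomized to" TAU. No agent is named.
- **SAP, Exploratory Hypothesis 6, heading:** TK patients "will demonstrate higher rates of Vivitrol initiation than patients assigned to TAU".
- **SAP, Exploratory Hypothesis 6, scoring rule:** there are two routes to an event. The first is an injection: "Patients will be considered MAT initiated if they receive a Vivitrol injection during the relevant time period". The second is a Vivitrol evaluation that ends in a referral elsewhere: "or if they attended an evaluation for Vivitrol and were deemed inappropriate for Vivitrol and referred to an alternative MAT".

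The SAP plans one logistic regression on this pooled yes/no outcome at 3 months and does not plan to report the two routes separately.

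Two other protocol statements bear on intent. Aim 3 asks whether the Toolkit "can reduce substance use and increase engagement with MAT". The section on expanding access to MAT gives the purpose as finding out whether exposed patients "become more likely to seek out and initiate MAT for alcohol SUDs".

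The PHMC Utilization Review (protocol section 7) lists the clinic data as separate items: whether the patient "attended an appointment for a Vivitrol evaluation, the determination of appropriateness for Vivitrol, and whether the patient actually received the initial dose" and any later doses.

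**The concern.** A patient who is evaluated, found unsuitable for Vivitrol and handed a referral has not, on that information, started any medication. The SAP nevertheless scores that patient as MAT initiated, alongside patients who received an injection. A patient who starts another MAT without passing through a Vivitrol evaluation is scored as not initiated. The figure would carry an initiation label without being an initiation rate for Vivitrol or for MAT.

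What is at stake is how the figure is used. Protocol section 5 says the pilot's effect sizes will be used to size a later, fully powered trial. Someone who took the Hypothesis 6 result at its label would plan that trial on a different event from the one measured. A larger sample would not correct this, because it concerns what is counted.

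**Working it through.** The documents give no rate, effect size or power for Hypothesis 6, so there is no plan figure to reproduce. The check compares the definitions and then works out how far they can diverge.

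**Step 1. Classify each patient path under the three texts (1 = event, 0 = no event).**

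| Path within 3 months | SAP rule | SAP heading: Vivitrol initiation | Protocol: MAT initiation |
|---|---|---|---|
| A. Vivitrol injection | 1 | 1 | 1 |
| B. Evaluated, unsuitable, referred; alternative started | 1 | 0 | 1 |
| C. Evaluated, unsuitable, referred; alternative not started | 1 | 0 | 0 |
| D. Non-Vivitrol MAT started outside that route | 0 | 0 | 1 |
| E. Evaluated, suitable; no injection, no other MAT | 0 | 0 | 0 |
| F. None of these | 0 | 0 | 0 |

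The rule departs from the SAP heading on paths B and C, and from the protocol on C and D.

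**Step 2. Write the error in an arm's rate.** Letters are patient counts and n = 25 is the planned number per arm (protocol section 4).

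- Against the SAP heading: (B + C)/n. This cannot be negative, provided all injections are captured.
- Against protocol Hypothesis 6: (C − D)/n. This can take either sign.
- One patient: 1/25 = 0.04, or 4 percentage points.

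**Step 3. Put in a range.** The counts are assumptions, because the documents supply none.

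- Heading, B + C from 0 to 2 per arm: each arm 0/25 to 2/25, or 0 to +8 points. TK-TAU difference: (0 − 2)/25 to (2 − 0)/25, or −8 to +8 points.
- Protocol, C and D each from 0 to 2 per arm: each arm (0 − 2)/25 to (2 − 0)/25, or −8 to +8 points. The difference could be off by up to 16 points either way, but only if all four counts sit at their limits.

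**Step 4. Show that the contrast can move either way.** Take equal injections, 3/25 in each arm, so the injection odds ratio is 1.00.

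- Add 2 referral-only patients in TK and 1 in TAU: (5/20)/(4/21) = 1.31.
- Add 1 in TK and 2 in TAU: (4/21)/(5/20) = 0.76.

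**Step 5. Compare with sampling error.** Assume 6/25 against 3/25, a difference of 0.24 − 0.12 = 12 points. The Newcombe 95% interval is −9.9 to +32.9 points, about 21 to 22 points either side of the estimate. It treats patients as independent, whereas counselors are the unit randomised (protocol section 6). If outcomes cluster by counselor, the true uncertainty is larger. The shifts in Step 3 are smaller than this.

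**The case against.** The strongest defence has four parts.

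- **The rule is explicit and prespecified.** Both routes stand in the same short paragraph as the heading, so an attentive reader of the SAP can see what is counted. This stands. It is why the composite should be kept. It does not make the label accurate, and without a breakdown by component a reader of the results could not recover the parts.
- **The second route has a rationale.** Aim 3 speaks of engagement, and the stated purpose includes seeking out MAT, so crediting a patient who sought Vivitrol and was unsuitable is reasonable. This stands as a reason to measure it. But the purpose statement names seeking and initiating as two steps, and the rule pools them under the name of the second. Nor does it measure seeking fully, since path E scores zero.
- **The route to harm is loose.** Nothing says Hypothesis 6 would be the later trial's primary outcome. It is also the only SAP hypothesis without a named effect size: Hypotheses 1 to 5 specify Cohen's d, while Hypothesis 6 specifies only logistic regression. This stands and limits the weight of the point.
- **The trial is an unpowered pilot of about 50 patients.** Sampling error exceeds any plausible misclassification. This also stands.

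A reader might go further and infer that the rule favours the Toolkit, since Toolkit counselors discuss medication and may send more patients to evaluation. The documents give no evaluation, referral or injection rates by arm, and TAU counselors are also trained on medication facts. Step 4 shows that the shift can go either way.

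**Conclusion.** The inconsistency is definite. As written, the SAP rule yields a rate that is broader than Vivitrol initiation and, compared with protocol Hypothesis 6, both too broad and too narrow. By definition, and with complete capture of injections, each arm's rate is equal to or above its Vivitrol initiation rate. The direction against the protocol hypothesis, and for the TK-TAU contrast, is not determined.

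The size is 4 points per misclassified patient per arm at the planned 25. The ranges above rest on assumed counts of 0 to 2. The planned number is used because the protocol reports that recruitment was ended by the funder and does not state the number achieved.

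Two stronger conclusions are not supported: that either arm is favoured, and that a later trial would be mis-sized by any particular amount. What is shown is a mislabelled estimate in one of six exploratory hypotheses. It should be fixed because the effect sizes have a stated later use and the remedy is cheap, but it belongs at the low end of points that need a change.

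**What to change.** 1. Reconcile the wording of Hypothesis 6 across the protocol, the SAP heading and the SAP rule.
2. Keep the prespecified composite as the planned analysis. Label it *Vivitrol injection, or evaluated and referred*, and do not present it as MAT initiation or as Vivitrol initiation.
3. Beside it, report by arm: (a) Vivitrol injection received; (b) Vivitrol evaluation attended; (c) referral to an alternative MAT, where recorded. Give proportions, and risk differences with intervals. Mark all three as added to the plan, and as post hoc if added after close-out.
4. Base any statement about Vivitrol initiation on row (a), without letting it silently replace the composite as the Hypothesis 6 result.
5. State that protocol Hypothesis 6 is only partly addressed, unless data already collected identify non-Vivitrol starts in both arms.

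The cost is wording and three table rows, with no new visit or question. The clinic record as described already separates attendance, suitability and doses. The downsides are fewer events and a less favourable rate for row (a). Row (c) may not be available, because a referral to another MAT is not among the clinic items the protocol lists.
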